**Table 1: Schedule of Additional Assessments for Subjects Enrolled in the Sub-study**

Study Assessments	Visit 1 a	OLE Treatment Period			
		Visit 2		Visits 3-4 (Months 1-2) b	Visit 5 (EOS/ET) Month 12 c
Study Day	1 a	15		30, 60	90
		Clinic	Phone		
Informed Consent	X				
Entry Criteria	X				
Issue/fit Embrace watch system and provide instructions on its use	X				
Perceived Stress Scale (PSS)	X			X	X
Ease of Use Questionnaire		X		X	X
EQ-5D-5L (QoL of parent/caregiver)	X			X	X
HADS (Affect of parent/caregiver)	X			X	X

Abbreviations: EOS/ET=End of Study/Early Termination; HADS=Hospital Anxiety and Depression Scale; OLE=open-label extension; PSS=Perceived Stress Scale; QoL=Quality of Life

Note: All other Study ZX008-1503 procedures must be completed as described in the main study protocol.

a Visit 1/Day 1 for sub-study ZX008-1503-SS01 corresponds to Visit 1/Day 1 for the main Study ZX008-1503.

b Subjects who continue for an additional 3 months will repeat Study Day 30 and 60 procedures on Study Days 90 and 120, and the end of study visit will be Study Day 150.

c At EOS/ET, subjects will be required to return the Embrace watch and study iPod.

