### 3.3 STUDY DURATION

The duration of the main Study ZX008-1503 for an individual who enters from Study ZX008-1501 or ZX008-1504 Cohort 2 is up to approximately 54 weeks. All subjects will receive ZX008 for up to approximately 52 weeks in Study ZX008-1503 and all subjects, including those who prematurely discontinue from the study, will undergo an up to 2-week taper of study medication, at the conclusion of the study. Subjects will be permitted to participate in the sub-study for the initial 12 weeks of participation in the main OLE study (ZX008-1503). Subjects may have the opportunity to extend participation in the sub-study for up to 24 weeks.

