- For each seizure, the peri-ictal EDA recording will be segmented from 60 minutes before detected seizure onset to 120 minutes afterward. A “significant EDA response” is declared when an increase in skin conductance level of more than 2 times the standard deviation of the pre-ictal baseline occurs. The time of the beginning of such an EDA response is defined as “EDA\_start,” the time of the maximum peak of the EDA response is defined as “EDA\_peak,” and the point in time following this peak, when the EDA falls below 10% of the peak amplitude is defined as “EDA\_end.” Significant EDA responses will be analyzed in terms of the amplitude of their EDA\_peak, the response duration, defined as the difference between “EDA\_end” and “EDA\_start,” and the natural logarithm of the area under the curve (AUC) of the rising phase (from “EDA\_start” to “EDA\_peak”) and of the total response (from “EDA\_start” to “EDA\_end”), ie, LogAUCrise and LogAUCtot. These measures will be examined to see if they vary over time with the treatment. Each of the measures will be evaluated for changes over time using a mixed model repeated measures (MMRE) that allows for a different intercepts for each subject (ie, a random effect) but a common slope over time (ie, a fixed effect).
- Skin-surface temperature changes will be averaged daily and compared over time, with separate comparisons made for “seizure-free” periods and for “pre-seizure periods.” The duration of these periods will be based on average 60-minute intervals, but may also be examined more with shorter intervals. Changes in skin-surface temperature over time will be evaluated using similar MMREs as described above for EDA endpoints.

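### The daily skin-temperature model names no serial correlation, random slope or robust standard error, so its slope will look too precise if neighbouring days are positively correlated

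*Combined protocol and SAP*

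**What the plan says.** Section 8.4 (Statistical Methods) sets the unit of analysis for temperature: "Skin-surface temperature changes will be averaged daily and compared over time, with separate comparisons made for" seizure-free and pre-seizure periods. It then carries the EDA model over: "Changes in skin-surface temperature over time will be evaluated using similar MMREs as described above for EDA endpoints". That model "allows for a different intercepts for each subject (ie, a random effect) but a common slope over time (ie, a fixed effect").

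The section does not give a residual covariance structure, a random slope, a robust standard error or a method for degrees of freedom. It calls the model a mixed model repeated measures, provides confidence intervals where warranted, and leaves the full description to a Statistical Analysis Plan to be finalized before database lock.

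Whether skin temperature changes with ZX008 treatment is a secondary exploratory objective (Section 2.2) and a secondary exploratory criterion (Section 8.3.2). Section 3.2 allows up to 20 subjects. On follow-up, Section 3.3 says "Subjects will be permitted to participate in the sub-study for the initial 12 weeks of participation in the main OLE study (ZX008-1503") and "Subjects may have the opportunity to extend participation in the sub-study for up to 24 weeks". The footnote to Table 1 says that, for subjects who extend, "the end of study visit will be Study Day 150". Section 8.2.2 admits a subject to the effectiveness analyses with one week of valid Embrace seizure data.

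**The concern.** A random intercept gives every pair of days within a subject the same correlation: days 1 and 2 are as alike as days 1 and 84. Daily means from a device on one wrist or ankle plausibly share weather, illness, routine and sensor placement with the days next to them. Correlation of that kind fades with distance in time, and an intercept cannot represent it. The model then credits each extra day with more information about the trend than it carries. This happens even if all subjects share exactly the same slope.

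A second omission acts in the same direction. The plan specifies "but a common slope over time (ie, a fixed effect"), so any real difference between subjects' trends is also left out of the standard error.

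At stake is a reported temperature trend on ZX008 whose stated precision the data do not support.

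**Working it through.** **Plan's own figure.** There is none to reproduce. The documents give no standard deviation, autocorrelation, significance level or standard error for this analysis.

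**Inputs from the documents.** N = 20 subjects at most (Section 3.2). The longest initial series is 12 × 7 = 84 days, and 24 × 7 = 168 days if extended (Section 3.3), although Table 1 ends the extension at Day 150. The model is random intercept plus common slope (Section 8.4).

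**Assumptions, not document figures.** Residual correlation is first-order autoregressive with day-to-day correlation ρ from 0 to 0.7. Subject slopes either do not differ, or have an SD equal to 0.5 residual SD of change over the whole period. Residuals in the fitted model are independent, because no structure is named.

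**Formulas.** Let x be the centred day number and n the number of days, so Sxx = n(n² − 1)/12. With complete daily data the planned slope is the within-subject least-squares slope.

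- Variance the model reports: s²/(N·Sxx)
- Actual variance: x′Vx/(N·Sxx²), where V has entries ρ^|j−k|, plus a slope-variance term if slopes differ
- Ratio r = √(actual/reported)
- Coverage of a nominal 95% interval = 2Φ(1.96/r) − 1; false-positive rate = 1 − coverage
- Long-series check: r ≈ √((1+ρ)/(1−ρ))

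**Serial correlation only, equal slopes, 84 days**

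| ρ | r | √((1+ρ)/(1−ρ)) | Coverage | False-positive rate |
|---|---|---|---|---|
| 0 | 1.00 | 1.00 | 95.0% | 5.0% |
| 0.3 | 1.35 | 1.36 | 85.2% | 14.8% |
| 0.5 | 1.71 | 1.73 | 74.8% | 25.2% |
| 0.7 | 2.33 | 2.38 | 60.0% | 40.0% |

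Simulation with 20 subjects, 84 days and no trend agrees: 4.9% at ρ = 0, 15.3% at 0.3 and 25.4% at 0.5 (5,000 runs each). At ρ = 0.7, separate simulations gave 38% to 42%.

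**Length of follow-up.** At 168 days the ratios are 1.36, 1.72 and 2.36 for ρ = 0.3, 0.5 and 0.7. The number of days hardly matters for this part.

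**Missing days.** With 30% of the 84 days missing at random, simulated false-positive rates are about 12%, 20% and 34% at ρ = 0.3, 0.5 and 0.7. With half missing they are about 10%, 16% and 28%.

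**Unequal slopes (SD 0.5, as assumed above).** With ρ = 0, r = 1.65 at 84 days (coverage 76.4%) and 2.11 at 168 days (64.7%). With ρ = 0.5 as well, r = 2.16 at 84 days (63.6%) and 2.53 at 168 days (56.1%).

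**Testing the remedies**

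- *Autoregressive residual alone.* With both problems present at 84 days the needed ratio is 2.16, and the residual structure supplies about 1.71. A shortfall of 2.16/1.71 = 1.26 remains.
- *Unweighted mean of per-subject slopes.* Sxx is 7 × 48/12 = 28 for a 7-day subject and 84 × 7,055/12 = 49,385 for an 84-day subject. With independent errors, the 7-day slope has a standard error √(49,385/28) ≈ 42 times larger. In simulation, three 7-day subjects among 20 made the standard error of the mean slope about ten times that of the planned slope.
- *Planned slope with a subject-clustered standard error and t on subjects minus one.* Simulated false-positive rates stayed at about 5% in the settings tried, including correlated days, unequal slopes, missing days and three 7-day subjects.

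**The case against.** The strongest reply is that the plan has not committed itself to independent residuals. It is silent on residual covariance, uses the term repeated measures, calls the temperature model only similar to the EDA one, and defers full methods to a later SAP. That is correct, and the SAP could still put this right. But the random intercept and common slope are the only structure in writing, and the common slope is explicit. An analyst who follows the text as it stands gets the standard error examined here.

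Three stronger readings are tempting, and the documents do not support them.

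- A reader might infer that daily values are treated as independent outright. They are not: the random intercept correlates all days within a subject, and independence holds only given that intercept.
- A reader might infer that the interval is certainly too narrow. That depends on a positive autocorrelation or on differing slopes, and the documents give neither. With both at zero the interval is correct.
- A reader might infer 84 to 168 consecutive values per subject. Those are maxima under complete wear. One week of data is enough for the analysis population, wear is asked for only as far as possible, and Table 1 ends the extension at Day 150. Pre-seizure values exist only around seizures, so the figures above do not describe that comparison.

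It can also be said that no test, significance level or slope interval is explicitly planned for temperature. That stands. Still, evaluating change over time with a mixed model produces a slope and a standard error, and any interval or p-value inherits the fault. Finally, the sub-study is open-label and all subjects receive ZX008, so even a correct standard error would not attribute a trend to the drug. That limits what the trend can show; it does not excuse a wrong standard error.

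**Conclusion.** The point holds in conditional form. Followed as written, Section 8.4 understates the uncertainty of the daily temperature slope whenever neighbouring days are positively correlated, and does so further if subjects' trends differ. Under the assumed ρ of 0.3 to 0.7 with 20 subjects and up to 84 days, the standard error is too small by about 1.35 to 2.3 times, and the false-positive rate at nominal 5% is about 15% to 40%. With 30% of days missing it is still about 12% to 34%. The direction follows from the model; the size rests on the assumed correlation and, where used, the assumed slope SD.

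This is worth correcting before the SAP is final. It concerns a secondary exploratory endpoint in a pilot of at most 20 subjects and does not touch the primary Ease of Use analysis.

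**What to change.** For the daily temperature trend, overall and in the seizure-free series, state in the SAP that the planned common slope will be reported with a subject-clustered (robust) standard error and a t reference distribution on the number of subjects minus one.

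A model-based alternative for the same purpose is a mixed model with a random slope, a within-subject residual correlation that depends on actual day spacing (continuous-time first-order autoregressive) and small-sample degrees of freedom. Spacing by actual day matters because gaps in wear are expected.

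Two simpler remedies should be avoided: an autoregressive residual without a random slope, which still forces a common slope, and an unweighted mean of per-subject slopes, which subjects with as little as one week of data would dominate.

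The cost is a few lines of SAP text and a small change in model code. The interval becomes wider. No data collection changes.

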## **9. DATA HANDLING PROCEDURES**

The investigator (or delegate) will maintain individual records for each subject. These records should include dates when a subject visited the study site, study-required information and data, and other notes as appropriate. These records constitute source data.

A CRF will be provided by the sponsor (or delegate) for each subject enrolled into the sub-study. Study site staff will enter data directly into the validated electronic data capture (EDC) system by completing the CRF via a secure internet connection. The investigator is

responsible for ensuring accurate and proper completion of the CRF for recording data according to the instructions given in the CRF.

All entries in the CRF must be backed up by the relevant source data at the study site. All source data will be kept according to all applicable regulatory requirements. Source data must be completed legibly for each subject enrolled into the sub-study and signed by the investigator (or delegate).

Data entry in the CRF must be completed in a timely manner so that they always reflect the latest observations on the subjects enrolled in the sub-study.

All Embrace data will be automatically captured and stored in a de-identified manner on a secure MySQL database and/or secured Amazon S3 buckets as part of the Empatica production server and analytics backend. Individual subjects will be tracked by the de-identified subject id assigned to each subject at the consent. No personally identifiable information will be directly linked to BPT data.

## **10. ETHICAL & REGULATORY CONSIDERATIONS**

The procedures set out in this study protocol are designed to ensure that the sponsor and the investigator abide by the principles of the current ICH GCP guideline on the conduct, evaluation and documentation of this study, as described in ICH Topic E6 Guideline. ICH GCP is an international ethical and scientific quality standard for designing, conducting, recording, and reporting studies that involve the participation of human subjects. Compliance with this standard provides public assurance that the rights, safety, and well-being of study subjects are protected, and that the clinical study data are credible.

The sub-study will also be carried out according to all applicable international and national regulatory requirements.

The sponsor and the investigator must inform each other (eg, during a study initiation visit, via e-mail, etc.) that all ethical and legal requirements have been met before the first subject is enrolled into the sub-study.

### **10.1 INFORMED CONSENT**

The investigator is responsible for obtaining a subject's written informed consent to participate in the sub-study.

A Subject Information Sheet and a master ICF will be prepared by the sponsor according to the provisions of ICH GCP and local legal requirements.

Before undergoing screening for possible enrollment into the sub-study, subjects must be informed, in an understandable form, about the nature, scope, and possible consequences of the study. This information must be given orally to subjects by a physician or medically qualified person (according to applicable regulatory requirements) who is well informed about the nature, scope, and possible consequences of the study. Written information about the study will also be provided in a Subject Information Sheet. The date on which this oral and written information on the study was provided to the subject, and by whom it was provided, must be documented in the ICF.

As specified in ICH GCP Section 4.8 and the US 21CFR Section 50.25, the informed consent discussion must emphasize that participation in the sub-study is voluntary and that subjects have the right to withdraw their consent at any time without giving a reason and without any disadvantage for their subsequent care.

Subjects must be given ample time and opportunity to inquire about details of the sub-study and to consider their participation in the sub-study. If, after reading the Subject Information Sheet and the ICF, consent is given to participate in the sub-study, then the ICF must be signed and personally dated by the subject and the person conducting the informed consent discussion (and an impartial witness, if required). The subject will be provided with a copy of the signed ICF.

Verification of the signed ICF will be recorded in the subject's CRF. The original signed ICF will be filed with the subject's records and/or in the Investigator Study File.

The Subject Information Sheet and ICF have to be approved by the IEC/IRB before they can be used in the study.

The Subject Information Sheet and ICF must be revised whenever important new information becomes available that may be relevant to the subject's consent. Any revision of these documents must be approved by the IEC/IRB before they can be used in the study. Subjects must be informed in a timely manner if new information becomes available that may be relevant to their willingness to continue participation in the study. The communication of this information should be documented by having all parties concerned sign and personally date the revised ICF.

### **Subject or Subject's Legally Acceptable Representative Unable to Read**

If a subject is unable to read, or if a legally acceptable representative is unable to read, an impartial witness should be present during the entire informed consent discussion. After the ICF and any other written information provided to the subject, parent or guardian has been read and explained to the subject or the subject's legally acceptable representative, and after the subject or the subject's legally acceptable representative has orally consented to the subject's

participation in the study and, if capable of doing so, has signed and personally dated the ICF, the witness should also sign and personally date the ICF. By signing the ICF, the witness attests that the information in the ICF and any other written information was accurately explained to, and apparently understood by, the subject or the subject's legally acceptable representative, and that informed consent was freely given by the subject or the subject's legally acceptable representative.

### **Assent for Subjects Under the Age of Consent (Pediatric Subjects)**

All subjects are under the age of consent (ie, pediatric subjects under 18 years of age); the written informed consent of a legally acceptable representative is required. Pediatric subjects who can understand the nature, scope, and possible consequences of the study must also give their assent, orally and/or in writing via the assent document, as appropriate. After the ICF and any other written information to be provided to subjects has been read and explained to the subject and the subject's legally acceptable representative, and after the subject and the legally acceptable representative have orally consented to the subject's participation in the study and, if capable of doing so, the subject has signed and personally dated the assent document, the legally acceptable representative should sign and personally date the ICF. By signing the ICF, the legally acceptable representative attests that the information in the ICF and any other written information was accurately explained to, and apparently understood by, the subject, and that assent was freely given by the subject.

## **10.2 REGULATORY CONSIDERATIONS AND INDEPENDENT ETHICS COMMITTEE/INSTITUTIONAL REVIEW BOARD**

The sponsor (or delegate) will submit the appropriate documents to all applicable competent regulatory authorities and IEC/IRBs, and will await all relevant approval before enrolling any subjects into the study. Written approval should mention the study protocol by study title, study number, and version date.

This study will be conducted under Investigational New Drug (IND) Application and documented in accordance with the applicable regulatory guidelines and requirements.

The sponsor (delegate) will ensure that the investigators conduct the study as stipulated in this study protocol and in accordance with all applicable regulatory requirements. The sponsor (delegate) is obliged to obtain evidence of the investigator's qualification to perform the clinical study. Therefore, the investigator has to provide a signed and dated copy of his or her professional curriculum vitae (prepared no more than 2 years beforehand and preferably written in English) before the start of the study, including information on his or her experience in conducting clinical studies according to ICH GCP and other applicable regulatory requirements.

Written notification of the identity and occupation of the members of the IEC/IRB is also required by the sponsor (delegate). Should the IEC/IRB be unwilling to provide this information, a letter stating that the committee was constituted in accordance with applicable regulatory requirements should be provided.

### **10.3        PROTOCOL COMPLIANCE**

The investigator must conduct the study in compliance with this sub-study protocol as agreed to by the sponsor and, if required, by any competent regulatory authority, and which has been approved by, or given a favorable opinion by, the IEC/IRB.

The investigator should not implement any deviation from, or changes to, the sub-study protocol without agreement by the sponsor (delegate) and prior review and documented approval or favorable opinion from the IEC/IRB of an amendment to the sub-study protocol. Exceptions include only cases of medical emergency to address immediate hazards to sub-study subjects, or when the changes involve only logistic or administrative aspects of the sub-study.

In the event of a medical emergency, the investigator at each site may institute any medical procedures deemed appropriate to address an immediate hazard to a subject without prior IEC/IRB approval or favorable opinion. As soon as possible, the implemented deviation or change, the reason(s) for it, and, if appropriate, the proposed study protocol amendment(s) should be submitted to:

- The sponsor (delegate) for agreement.
- The IEC/IRB for review and approval or favorable opinion (if required).
- The applicable competent regulatory authority (if required).

At the earliest opportunity, the investigator (or delegate) must inform the sponsor (delegate) about any notable protocol deviations and explain any deviation from the approved sub-study protocol in the CRF and/or in the Protocol Deviation Log, if applicable.

## **11.        ADMINISTRATIVE ASPECTS**

The administrative aspects of this sub-study are described in the main Study ZX008-1503 protocol.

**13. APPENDICES**

PUBLIC COPY  
This document cannot be used to support any marketing authorization application and any extensions or variations thereof.

## APPENDIX 1 – LIKERT EASE OF USE QUESTIONNAIRE

Over the last week, using the Embrace watch was:

- 1 – Very difficult
- 2 – Difficult
- 3 – Neutral
- 4 – Easy
- 5 – Very easy

Over the last week, using the Mate App was:

- 1 – Very difficult
- 2 – Difficult
- 3 – Neutral
- 4 – Easy
- 5 – Very easy

Over the last week, using the Alert App was:

- 1 – Very difficult
- 2 – Difficult
- 3 – Neutral
- 4 – Easy
- 5 – Very easy

